### 6.3 Dose Modifications/Delays

If the patient experiences unacceptable toxicities, treatment with the study drug should be suspended until the toxicities return to  $\leq$  CTCAE grade 1 (or baseline). Dose modification may be required upon treatment resumption, see below.

Patients whose treatment is interrupted or permanently discontinued due to an adverse event or abnormal laboratory value should be followed at least once a week for 4 weeks, and subsequently at 4-week intervals, until resolution or stabilization of the event, whichever comes first. If a patient requires a dose delay of  $>21$  days from the intended day of the next scheduled dose, then the patient must discontinue the study. All patients will be followed for adverse events and serious adverse events for 28 days following the last dose of AUY922.

Toxicity will be assessed using the NCI-CTC for Adverse Events, version 4.0 (CTCAE v4.0)

For patients who are unable to tolerate the protocol-specified dosing schedule, schedule adjustments are permitted. This includes the ability to skip a week of dosing if needed up to once per cycle.

Dose reduction levels are listed in Table 4 and specific instructions for holding drug, reducing doses, and managing toxicities are listed in Table 5. Only two dose level reductions are allowed per patient.

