**Table 5. Criteria for Interruption, Dose Reduction and Re-Initiation of AUY922**

| Recommended Dose Modifications for AUY922                                |   |
|--|---|
| Worst Toxicity
CTCAE Grade a unless otherwise
specified | At any time during a cycle of AUY922
(including intended day of dosing)  |
| No toxicity   | Maintain dose level  |
| Diarrhea  |   |
| Grade 1 (see Section 6.2 for recommended treatment algorithm)            | Maintain dose level   |
| Grade 2
(see Section 6.2 for recommended treatment algorithm)         | Omit dose administration until recovery to Grade 1 or baseline, then continue AUY922 at:
- current dose level if grade 2 toxicity persisted ≤ 7 days.
- one dose level lower if grade 2 toxicity persisted > 7 days   |
| Grade 3
(see Section 6.2 for recommended treatment algorithm)         | Omit dose administration until recovery to Grade 1 or baseline then decrease the next scheduled dose by 1 dose level.   |
| Grade 4
(see Section 6.2 for recommended treatment algorithm)         | Omit dose administration until recovery to Grade 1 or baseline then:
- if grade 4 toxicity lasted ≤ 24 hours, may resume AUY922 but decrease the next scheduled dose by 1 dose level.
- In the event Grade 4 toxicity lasted >24 hours despite maximal medical attention, permanently discontinue treatment.

If grade 4 toxicity recurs upon re-exposure, permanently discontinue treatment. |

| Recommended Dose Modifications for AUY922  |   |
|---|---|
| Worst Toxicity
CTCAE Grade a unless otherwise
specified                                       | At any time during a cycle of AUY922
(including intended day of dosing)  |
| Hematological  |   |
| Neutropenia (ANC)
Grade 1 (ANC < LLN - $1.5 \times 10^9/L$ ) or
Grade 2 (ANC < $1.5 - 1.0 \times 10^9/L$ ) | Maintain dose level   |
| Grade 3 (ANC < $1.0 - 0.5 \times 10^9/L$ )  | Omit dose administration until resolved to $\leq$ grade 1,

 
• If resolved in <math>\leq</math> 7 days, then maintain dose level
 
• If resolved in <math>></math> 7 days, then decrease by 1 dose level
 
       |
| Grade 4 (ANC < $0.5 \times 10^9/L$ )  | Omit dose administration until resolved to $\leq$ grade 1, then
decrease by 1 dose level   |
| Febrile neutropenia   | Omit dose administration until resolved, then decrease by 1
dose level   |

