| Thrombocytopenia   |   |
| Grade 1 (PLT < LLN - $75 \times 10^9/L$ )   | Maintain dose level   |
| Grade 2 (PLT < $75 - 50 \times 10^9/L$ ) or
Grade 3 (PLT < $50-25 \times 10^9/L$ )                                   | Omit administration dose until resolved to $\leq$ grade 1, then:

 
• If resolved in <math>\leq</math> 7 days, then maintain dose level
 
• If resolved in <math>></math> 7 days, then decrease by 1 dose level
 
 |
| Grade 4 (PLT < $25 \times 10^9/L$ )   | Omit administration dose until resolved, then decrease by 1
dose level   |
| Renal  |   |
| Serum creatinine
( $< 2 \times$ ULN)  | Maintain dose level   |
| ( $2 - 3 \times$ ULN)   | Omit dose administration until resolved to $\leq$ grade 1, then

 
• If resolved in <math>\leq</math> 7 days, then maintain dose level
 
• If resolved in <math>></math> 7 days, then decrease by 1 dose level
 
  |
| Grade 3 ( $>3.0$ baseline; $> 3.0 - 6.0 \times$ ULN) or
Grade 4 ( $> 6.0 \times$ ULN)                                | Omit dose administration and permanently discontinue patient
from study treatment  |
| Hepatic  |   |
| Bilirubin
( $< 2 \times$ ULN)   | Maintain dose level   |
| ( $2 - 3 \times$ ULN)   | Omit dose administration until resolved to $\leq$ grade 1, then

 
• If resolved in <math>\leq</math> 7 days, then maintain dose level
 
• If resolved in <math>></math> 7 days, then decrease by 1 dose level
 
  |
| Grade 3 ( $> 3.0 - 10.0 \times$ ULN)  | Omit dose administration until resolved to $\leq$ grade 1, then
decrease by 1 dose level   |
| Grade 4 ( $> 10.0 \times$ ULN)  | Omit dose administration and permanently discontinue patient
from study treatment  |

| Recommended Dose Modifications for AUY922  |   |
|---|---|
| Worst Toxicity
CTCAE Grade a unless otherwise
specified   | At any time during a cycle of AUY922
(including intended day of dosing)  |
| AST or ALT
Grade 1 (>ULN - 3.0 x ULN) or
Grade 2 (Asymptomatic with ALT >3.0 - 5.0 x
ULN; >3 x ULN with the appearance of
worsening of fatigue, nausea, vomiting, right
upper quadrant pain or tenderness, fever,
rash, or eosinophilia) | Maintain dose level   |

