## 10. ADVERSE EVENT REPORTING REQUIREMENTS

### 10.1 Definitions

#### 10.1.1 Adverse Event (AE)

An adverse event (AE) is any undesirable sign, symptom or medical condition or experience that develops or worsens in severity after starting the first dose of study treatment or any procedure specified in the protocol, even if the event is not considered to be related to the study.

Abnormal laboratory values or diagnostic test results constitute adverse events only if they induce clinical signs or symptoms or require treatment or further diagnostic tests.

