#### 11.1.2 Data Submission

**Table 8. Schedule for completion and submission of eCRFs to the QACT**

| Form                         | Submission Timeline  |
|------------------------------|--|
| Eligibility Checklist        | Complete prior to registration with QACT                                       |
| On Study Form                | Within 14 days of registration   |
| Baseline Assessment Form     | Within 14 days of registration   |
| Treatment Form               | Within 10 days of the last day of the cycle                                    |
| Adverse Event Report Form    | Within 10 days of the last day of the cycle                                    |
| Response Assessment Form     | Within 10 days of the completion of the cycle required for response evaluation |
| Off Treatment/Off Study Form | Within 14 days of completing treatment or being taken off study for any reason |
| Follow up/Survival Form      | Within 14 days of the protocol defined follow up visit date or call            |

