### **13.5 Safety of Treatment**

A summary of the adverse events and their attributed relatedness to treatment will be provided. All patients will be included in the safety analyses

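### The adverse event definition does not name dose modification as a trigger, so asymptomatic laboratory toxicity that holds or reduces AUY922 can be missing from the safety summary or counted differently between sites

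*Combined protocol and SAP*

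**What the plan says.** Section 10.1.1 limits when a laboratory finding becomes an adverse event: "Abnormal laboratory values or diagnostic test results constitute adverse events only if they induce clinical signs or symptoms", and the same sentence adds "or require treatment or further diagnostic tests". There are thus three routes in: symptoms, treatment, or further testing. Neither CTCAE grade nor a change in dosing is named.

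Table 5 in Section 6.3 acts on laboratory values without asking for symptoms. Neutropenia of grade 3 or 4 has the instruction "Omit dose administration until resolved to" grade 1 or lower, with a reduction for grade 4 or slow recovery. Grade 4 thrombocytopenia has "Omit administration dose until resolved, then decrease by 1" dose level. Creatinine of grade 3 or 4 and bilirubin of grade 4 have "Omit dose administration and permanently discontinue patient". Grade 3 or 4 AST/ALT leads to a hold, and to a reduction for grade 4 or slow recovery.

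The text of Section 6.3 speaks of treatment interrupted or stopped "due to an adverse event or abnormal laboratory value", which sets the two side by side as separate causes.

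The planned safety analysis in Section 13.5 reads: "A summary of the adverse events and their attributed relatedness to treatment will be provided". It mentions no laboratory-grade table and no dose-modification table. Table 8 lists eight forms, among them the "Adverse Event Report Form", a Treatment Form and an Off Treatment/Off Study Form. None is titled as a laboratory form.

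**The concern.** Safety and tolerability is a secondary objective (Section 1.3), and Section 6.1 names bone marrow among the main target organs. Cytopenias are therefore anticipated, and a cytopenia can be silent. If the only planned safety output is a summary of adverse events, and a silent laboratory toxicity that changed a patient's dosing need not be one, the summary can understate how often the drug could not be given as planned. With three clinics (Section 13.2) and at most 29 patients, two sites could also handle the same finding differently while both comply with the protocol.

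**Working it through.** The plan states no figure on this point, so the check is mainly a comparison of provisions, followed by an illustration.

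**Step 1: one patient taken through the rules.** Suppose a patient has grade 3 neutropenia, with no fever, no symptoms and no growth factor or other treatment.
- Table 5: the dose is omitted. If the count recovers to grade 1 or lower within 7 days, the dose level is kept; if it takes longer, the dose is reduced one level.
- Study calendar (Section 8): haematology and biochemistry are already scheduled at every dosing visit (days 1, 8 and 15), so the recheck can fall on a planned visit.
- Section 6.3 asks for at least weekly follow-up for 4 weeks after such an interruption, which is the same rhythm as the dosing visits.
- Section 10.1.1: symptoms, no; treatment, no; further testing, only if a scheduled test counts as further. The text does not say.

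The same reasoning applies to an asymptomatic AST/ALT rise of grade 3.

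**Step 2: can the information reach the results by another route?**

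| Consequence of the laboratory value | Other route | What that route gives |
|---|---|---|
| Hold or reduction | Treatment Form (Table 8), contents not described | Possibly recorded; no analysis planned |
| Permanent stop | Reason on a CRF (Section 5.8), Off Treatment/Off Study Form (Table 8), discontinuation summary (Section 13.3) | Counted with a reason, but not as graded, attributed toxicity |
| QTcF of 501 msec or more | Hourly ECGs (Table 5) | Meets the further-testing limb |
| QTcF 481 to 500 msec in cycle 1 | Extended ECG monitoring (Table 5) | Meets the further-testing limb |
| Low potassium or magnesium | Replacement (Table 5, footnote b) | Meets the treatment limb |

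Section 10.2 records events detected by laboratory test, but only once they are adverse events. Section 11.2 gives the monitoring committee laboratory values on request. The gap is therefore clearest for holds and reductions.

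**Step 3: illustration of size.** Let q be the assumed proportion of patients whose only dose-changing toxicity is a laboratory value meeting none of the three limbs. With N = 29 (Section 13.2), the expected number uncounted is 29q, and the probability of at least one is 1 − (1 − q)^29.

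| q (assumed) | 29q | Probability of at least one |
|---|---|---|
| 2% | 0.58 | 0.44 |
| 5% | 1.45 | 0.77 |
| 10% | 2.9 | 0.95 |
| 20% | 5.8 | 0.998 |

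As a single hypothetical case, 3 affected patients give 3/29 = 10.3% (exact 95% interval 2.2% to 27.4%). If none met a limb, the adverse event table would show 0/29, with an upper limit of 1 − 0.025^(1/29) = 11.9%.

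**The case against.** Four arguments can be made against the point.

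1. **Most laboratory holds need repeat testing.** Recovery to grade 1 can only be shown by a new test, and Section 6.3 requires follow-up, so the further-testing limb would usually be met. This is a fair reading, but not a compelled one, since the tests are already scheduled. It turns an omission into an ambiguity, which still produces uneven counting.

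2. **The protocol elsewhere treats the laboratory rows as adverse events.** The introduction to Section 6.2 describes Section 6.3 as covering general adverse events. Table 5 heads its rows by worst CTCAE toxicity and, after the laboratory and QTcF rows, has a row for other adverse events, which implies that those before it are adverse events too. This stands as evidence of intent. It conflicts with the paired wording in Section 6.3 and does not override the explicit restriction in Section 10.1.1.

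3. **Section 10.4.1 has its own grade-based reporting.** It reaches certain grade 4 events and unexpected, possibly related grade 2 and 3 events, and does not repeat the symptom condition. It may catch some cases. It does not reach an expected grade 3 value that holds or reduces dosing.

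4. **The forms' fields are not in the documents.** The lack of a form titled for laboratory results does not show that the values go unrecorded. This is correct.

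A reader might infer that the definition excludes every asymptomatic laboratory abnormality, or that nothing else in the plan captures them. The documents support neither. Abnormalities that need treatment or further tests count, and stops are recorded with a reason and summarised. Nor is there a demonstrated gap for QTcF or electrolytes.

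**Conclusion.** The point holds in a limited form. Section 10.1.1 does not make a dose change a trigger, Table 5 changes dosing on laboratory grade alone, and Section 13.5 reports adverse events only. An asymptomatic laboratory toxicity that holds or reduces AUY922 can therefore be absent from the safety summary or be counted unevenly across the three sites. For permanent stops the loss is smaller: the stop is reported with a reason, but not as graded, attributed toxicity.

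The size cannot be determined. The documents give no laboratory toxicity rates, so the values of q and the 3/29 case are illustrations only, and the 0/29 comparison also assumes that none of the three patients was captured by any other route. The primary endpoint and the two-stage decision are unaffected. This is an inexpensive clarification worth making for a secondary objective.

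**What to change.** - **Section 10.1.1:** add that a laboratory abnormality leading to omission, delay, reduction or discontinuation of AUY922 is recorded as an adverse event with its CTCAE grade, whether or not it causes symptoms or needs treatment or further tests. This removes the dependence on how a scheduled recheck is read.
- **Section 13.5:** add a table of worst on-study CTCAE grade for each Table 5 laboratory parameter (neutrophils, platelets, creatinine, bilirubin, AST/ALT), and a summary of dose omissions, delays, reductions and discontinuations with reasons.
- **Data collection:** confirm that the forms in Table 8 carry the grades and the reasons for dose modification that these tables need.

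The tests are already scheduled, and no dose or clinical rule changes. The cost is slightly more data entry and one or two more tables, and the reported toxicity may look slightly less favourable.

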#### 10.1.2 Serious adverse event (SAE)

A serious adverse event (SAE) is any adverse event, occurring at any dose and regardless of causality that:

- Results in death
- Is life-threatening. Life-threatening means that the person was at immediate risk of death from the reaction as it occurred, i.e., it does not include a reaction which hypothetically might have caused death had it occurred in a more severe form.
- Requires or prolongs inpatient hospitalization (i.e., the event required at least a 24-hour hospitalization or prolonged a hospitalization beyond the expected length of stay). Hospitalization admissions and/or surgical operations scheduled to occur during the study period, but planned prior to study entry are not considered SAEs if the illness or disease existed before the person was enrolled in the trial, provided that it did not deteriorate in an unexpected manner during the trial (e.g., surgery performed earlier than planned).
- Results in persistent or significant disability/incapacity. Disability is defined as a substantial disruption of a person's ability to conduct normal life functions.
- Is a congenital anomaly or birth defect; or

- Is an important medical event when, based upon appropriate medical judgment, it may jeopardize the participant and require medical or surgical intervention to prevent one of the outcomes listed above. Examples of such medical events include allergic bronchospasm requiring intensive treatment in an emergency room or at home; blood dyscrasias or convulsions that do not result in inpatient hospitalization, or the development of drug dependency or drug abuse.

Events **not** considered to be serious adverse events are hospitalizations for:

- routine treatment or monitoring of the studied indication, not associated with any deterioration in condition, or for elective procedures
- elective or pre-planned treatment for a pre-existing condition that did not worsen
- emergency outpatient treatment for an event not fulfilling the serious criteria outlined above and not resulting in inpatient admission
- respite care

#### 10.1.3 Expectedness

Adverse events can be 'Expected' or 'Unexpected.'

##### 10.1.3.1 Expected adverse event

Expected adverse events are those that have been previously identified as resulting from administration of the agent. For the purposes of this study, an adverse event is considered expected when it appears in the Investigator's Brochure or is included in the informed consent document as a potential risk.

##### 10.1.3.2 Unexpected adverse event

For the purposes of this study, an adverse event is considered unexpected when it varies in nature, intensity or frequency from information provided in the Investigator's Brochure or when it is not included in the informed consent document as a potential risk.

#### 10.1.4 Attribution

Attribution is the relationship between an adverse event or serious adverse event and the study treatment. Attribution will be assigned as follows:

- Related – The AE is clearly or may possibly be related to the study treatment.

- Unrelated – The AE is unlikely or clearly not related to the study treatment.

## 10.2 Procedures for AE and SAE Recording and Reporting

Reporting Participating investigators will assess the occurrence of AEs and SAEs at all participant evaluation time points during the study.

All AEs and SAEs whether reported by the participant, discovered during questioning, directly observed, or detected by physical examination, laboratory test or other means, will be recorded in the participant's medical record and on the appropriate study-specific case report forms.

The descriptions and grading scales found in the CTEP NCI Common Terminology Criteria for Adverse Events (CTCAE) version 4.0 will be utilized for AE reporting, and can be found on the CTEP website at:

[http://ctep.cancer.gov/protocolDevelopment/electronic\\_applications/ctc.htm](http://ctep.cancer.gov/protocolDevelopment/electronic_applications/ctc.htm).

## 10.3 Reporting Requirements

Each participating investigator is required to abide by the reporting requirements set by the DF/HCC. The study must be conducted in compliance with FDA regulations, local safety reporting requirements, and reporting requirements of the principal investigator.

## 10.4 Reporting to the Study Sponsor

### 10.4.1 Serious Adverse Event Reporting

All serious adverse events that occur after the initial dose of study treatment, during treatment, or within 30 days of the last dose of treatment must be reported to the DF/HCC Overall Principal Investigator [name] (who is the Study Sponsor) on the local institutional SAE form. This includes events meeting the criteria outlined in Section 10.1.2, as well as the following:

- Grade 2 (moderate) and Grade 3 (severe) events that are unexpected and at least possibly related/associated with the intervention.
- All Grade 4 (life-threatening or disabling) events that are unexpected or not specifically listed in the protocol as not requiring reporting.
- All Grade 5 (fatal) events while the participant is enrolled and actively participating in the trial OR when the event occurs within 30 days of the last study intervention.

**Note:** If the participant is in long term follow up, report the death at the time of continuing review.

Participating investigators must report each serious adverse event to the DF/HCC Overall Principal Investigator within 24 hours of learning of the occurrence. In the event that the participating investigator does not become aware of the serious adverse event immediately (e.g., participant sought treatment elsewhere), the participating investigator is to report the event within 24 hours after learning of it and document the time of his or her first awareness of the adverse event. Report serious adverse events by telephone, email or facsimile to:

[name], MPH  
Massachusetts General Hospital Cancer Center

[REDACTED]  
[REDACTED]  
Email: [[contact]](mailto:[contact])

and

[name]

[REDACTED]  
[REDACTED]  
Within the following 24-48 hours, the participating investigator must provide follow-up information on the serious adverse event. Follow-up information should describe whether the event has resolved or continues, if and how the event was treated, and whether the participant will continue or discontinue study participation.

#### **10.4.2 Non-Serious Adverse Event Reporting**

Non-serious adverse events will be reported to the DF/HCC Overall Principal Investigator on the toxicity Case Report Forms.

### **10.5 Reporting to the Institutional Review Board (IRB)**

Investigative sites within DF/HCC will report all serious adverse events directly to the DFCI Office for Human Research Studies (OHRS).

### **10.6 Reporting to the Food and Drug Administration (FDA)**

The DF/HCC Overall Principal Investigator, as holder of the IND, will be responsible for all communication with the FDA. The DF/HCC Overall Principal Investigator will report to the FDA, regardless of the site of occurrence, any adverse event that is

serious, unexpected and reasonably related (i.e., possible, probable, definite) to the study treatment.

Unexpected fatal or life-threatening experiences associated with the use of the study treatment will be reported to FDA as soon as possible but in no event later than 7 calendar days after initial receipt of the information.

All other serious unexpected experiences associated with the use of the study treatment will be reported to FDA as soon as possible but in no event later than 15 calendar days after initial receipt of the information.

Events will be reported to the FDA by telephone ([name]) or by fax ([name]) using Form FDA 3500A (Mandatory Reporting Form for investigational agents) or FDA Form 3500 (Voluntary Reporting Form for commercial agents). Forms are available at <http://www.fda.gov/medwatch/getforms.htm>.

